Contrasting immune responses to influenza and RSV In a mouse model of influenza infection, viral load falls as soon as CTLs appear in the lung¹³ and effector memory CTLs act rapidly on re-challenge to recruit T cells to then expand and form a new effector pool. Along with the humoral response against HA and NA, this leads to protective immunity and re-infection with the same strain of influenza does not occur¹⁴. In contrast, infection with RSV does not confer full protective immunity. Almost all children will have seroconverted to RSV by 24 months of age, but re-infection is common throughout life. This occurs despite persistent antibodies against the relatively conserved F protein which are cross-reactive against the different serogroups of RSV¹⁵. In human experimental challenge studies, where adults naturally infected with RSV were later challenged 6 times with a similar laboratory strain, 73% could be re-infected and 50% re-infected twice or more¹⁶. Re-infection took place at a rate of 25% even in those subjects with the highest levels of IgG and IgA against F and G proteins within as little as 2 months. These differences are likely to be due to differential immune responses against influenza and RSV and may be quantitative or functional. In adult blood and lung, influenza-specific memory T cells are 2-4 times more frequent than those specific for RSV^{17,18}, while analysis of cytokine responses in the nasopharyngeal aspirates of infected children show higher levels of IFN- γ and decreased IL-4 and IL-5 in influenza compared with RSV¹⁹.

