1.8. Exclusion criteria

Chronic respiratory disease (asthma, COPD, rhinitis, sinusitis) in adulthood

Inhaled bronchodilator or steroid use within the last 12 months

Use of any medication or other product (prescription or over-the-counter) for symptoms of rhinitis or nasal congestion within the last 3 months

Acute upper respiratory infection (URI or sinusitis) in the past 6 weeks

Smoking in the past 6 months OR >5 pack-year lifetime history

Subjects with allergic symptoms present at baseline

Clinically relevant abnormality on chest X-ray

Any ECG abnormality

Those in close domestic contact (i.e. sharing a household with, caring for, or daily face to face contact) with children under 3 years, the elderly (>65 years), immunosuppressed persons, or those with chronic respiratory disease

Subjects with known or suspected immune deficiency

Receipt of systemic glucocorticoids (in a dose \geq 5 mg prednisone daily or equivalent) within one month, or any other cytotoxic or immunosuppressive drug within 6 months prior to challenge

Known IgA deficiency, immotile cilia syndrome, or Kartagener's syndrome

History of frequent nose bleeds

Any significant medical condition or prescribed drug deemed by the study doctor to make the participant unsuitable for the study

Pregnant or breastfeeding women

Positive urine drug screen

[figure not shown]
Detectable baseline antibody titres against influenza challenge strains

Influenza arm only: history of hypersensitivity to eggs, egg proteins, gentamicin, gelatin or arginine, or with life-threatening reactions to previous influenza vaccinations.

All women of childbearing age will have a **pregnancy test performed prior to virus inoculation** to exclude pregnancy and be required to use contraception **throughout the study**.

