1.13.3. Nasal Lavage

Nasal lavage is performed using the following technique:

- 5mL of 0.9% saline is introduced into each nostril using a syringe attached to a nasal olive with the subject sitting with the head tilted forward
- The saline is then washed in and out of the nose approximately 10 times by alternately withdrawing and advancing the plunger of the syringe while the subject maintains a tight seal between the nasal olive and the nostril; the aim is to recover ~80% of the saline from the nose
- The fluid is then aliquotted into sterile microfuge tubes and centrifuged for analysis of cells

Lavage fluid will later be analysed to quantify the degree of RSV or influenza shedding. Multiplex PCR will be performed on the pre-inoculation lavage and post-inoculation lavage collected during the study to exclude the presence of other respiratory viruses. Supernatants will be frozen and stored at -80°C. Further details are given in the SOP Human Sampling Procedures for Challenge Study.

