Based on pilot data from de Bree et al., we calculate that a sample size of 16 in each arm will be sufficient to find a difference of 1.4 between epitope-specific T cell counts in blood and lung, with 80% power using a 2-sided unpaired t-test with 5% significance level (where the variability in each group is 1.3). T cell numbers will be compared between RSV and influenza using an unpaired t-test (if normality of the T cell distribution, or its transformation, is satisfactory as assessed by histogram with q-qplot and Shapiro-Wilks test) or a Mann-Whitney test (if normality is not satisfactory). We will perform microarray analysis on each of 6 patients prior to inoculation and at 3 post-baseline timepoints. Our main analysis will identify differentially expressed genes between influenza and RSV at each post-baseline timepoint. The sample size, calculated using the size package from bioconductor which provides pilot data of gene expression variability from the U95 package, predicts that 6 individuals in each group will give us 80% power to detect a potential fold change of 3 in up to 67% of the genes with a Bonferroni multiple testing correction with a genome-wide 5% significance level.

Quantitative assessments of symptom scores, lung function, virus load, leukocyte numbers and inflammatory markers will be compared within subjects to determine differences between baseline and during infection. Intra-subject differences will be analysed using ANOVA and 2-tailed paired Student's t-tests or Wilcoxon signed rank test as appropriate. Correlations between inflammatory cell, illness severity, viral load and leukocyte counts will be examined using Spearman's rank correlations to investigate possible causal relationships.

Data and all appropriate documentation will be stored for a minimum of 10 years after the completion of the study, including the follow-up period according to Imperial College London policy.

REGULATORY ISSUES

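### The RSV-versus-influenza T-cell test names no analysis set and infection is never defined, so it is unsettled how inoculated but uninfected participants count, and power at 16 per arm assumes nearly all are infected

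*Combined protocol and SAP*

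**What the plan says.** The primary objective (section 1.3) is to test whether RSV and influenza lead to different T-cell responses. Hypothesis 2 in section 1.2 contrasts influenza responses with those that RSV infection elicits. In Statistics and Data Analysis, the matching test is: "T cell numbers will be compared between RSV and influenza using an unpaired t-test", with Mann-Whitney as the fallback. No analysis set is attached to it.

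The sample size statement reads "we calculate that a sample size of 16 in each arm will be sufficient". Its target is a gap of 1.4, worded as blood against lung. It assumes a variability of 1.3 per arm and aims for 80% power from an unpaired t-test at the two-sided 5% level.

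Other places that touch on infection:
- Section 1.13.3: "Lavage fluid will later be analysed to quantify the degree of RSV or influenza shedding". It gives no threshold and no link to an analysis.
- Section 1.18 defines a clinical cold from symptoms. No analysis uses that definition.
- Section 1.10.2 uses the verb infect for the act of inoculation.
- The within-subject analyses compare baseline with a period of infection, as if every participant has one.
- Assessment and Follow-up ends the study on numbers recruited, not numbers infected. No replacement rule is given.
- Section 1.23 keeps participants in the analysis if they are given alternative treatment. It does not address those who were never infected.
- Section 1.1, on earlier experimental RSV challenge of adults who had already been naturally infected: over six challenges, "73% could be re-infected and 50% re-infected twice or more".

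**The concern.** In a challenge study, inoculation is the intervention and infection is an outcome. The scientific question is what T cells do in response to infection, but the test is written for arms. An inoculated participant who is never infected should show roughly a resting count. If that participant is included, the arm mean becomes a mixture of responders and non-responders, weighted by the attack rate. Two things can follow: a real difference between the viruses is diluted, or a difference in attack rate appears as a difference in T-cell response. If that participant is excluded, the comparison rests on fewer than 16 per arm and on a subset formed after inoculation. The plan chooses neither course, so the choice could be made after the T-cell data are known.

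Non-infection is foreseeable. In the background series, 100% − 73% = 27% were never re-infected over six challenges, and the rate was 25% in those with the highest antibody. This shows that inoculation does not always infect. It does not forecast the rate in this trial.

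**Working it through.** **Inputs from the plan.** Difference 1.4, variability 1.3 (read as a standard deviation), two-sided 5%, unpaired t-test, 16 per arm. The statement words the 1.4 as blood versus lung; here it is applied to the RSV-versus-influenza test that it is used to size.

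**Reproducing the plan's figure.** The normal approximation gives n = 2(1.96 + 0.84)² × 1.3² / 1.4² = 13.5, so 14 per arm. The exact noncentral t gives 15 (81.2% power). Dividing by 0.955 for Mann-Whitney gives 15 / 0.955 = 15.7, so 16. The stated 16 is reproduced, and exact t power at 16 is 83.8%. Reading 1.3 as a variance gives 12 per arm, so the standard deviation reading fits better.

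**If only infected participants are compared.** Noncentrality = 1.4 / (1.3 × √(1/n₁ + 1/n₂)), with n₁ + n₂ − 2 degrees of freedom. For 13 versus 8 this is 1.4 / (1.3 × 0.449) = 2.40. The attack rates below are assumed.

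| Assumed attack rate | Infected per arm, of 16 | Power | Inoculated per arm to have 16 infected |
|---|---|---|---|
| 100% | 16 | 83.8% | 16 |
| 90% | 14 | 78.3% | 18 |
| 80% | 13 | 75.0% | 20 |
| 70% | 11 | 67.1% | 23 |
| 60% | 10 | 62.5% | 27 |
| 50% | 8 | 51.8% | 32 |
| 80% and 50% | 13 and 8 | 62.3% | 20 and 32 |

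Power is 81.2% at 15 per arm and 78.3% at 14, so 80% is lost once fewer than 15 per arm are infected.

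**If all inoculated participants are compared (illustration only).** Assume the same resting mean for both viruses, SD 1.3, and a response m added only in the infected fraction p. The arm mean is then p × m above rest and the arm variance is 1.3² + p(1 − p)m². Rejection rates come from simulating the t-test with 16 per arm.

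*Identical responses among the infected (nominal 5%).* The expected difference is (p_influenza − p_RSV) × m.
- Equal rates (70/70): 5%.
- Rates 10 points apart (70/60 or 60/50), m from 1.4 to 2.8: about 6-7%.
- 80% versus 50%: about 13%, 18% and 25% for m = 1.4, 2.0 and 2.8. At m = 2.8 the spurious difference is 0.30 × 2.8 = 0.84.

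*True difference of 1.4 among the infected (2.8 versus 1.4).*
- All infected: 84% power.
- 70/70: expected difference 0.7 × 1.4 = 0.98. Arm variances are 1.69 + 0.21 × 2.8² = 3.34 and 1.69 + 0.21 × 1.4² = 2.10. The standard error is √((3.34 + 2.10)/16) = 0.58, and power is about 37%.

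*Sensitivity to the resting assumption.* Suppose instead that influenza-specific counts are already 1.4 higher at rest and infection adds 1.4 in both arms. At 70/70 the expected difference stays at 1.4, each arm variance is 2.10, the standard error is √(2 × 2.10/16) = 0.51, and power is about 75%. The power loss therefore depends heavily on where the 1.4 comes from.

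**Arrays.** With 6 per group, one uninfected participant is 1/6 = 17% of a group.

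**The case against.** The strongest reply is that the text does not put uninfected participants into the test. It names no analysis set, and both the hypotheses and the within-subject paragraph speak of infection, so an infected-only analysis may be what was meant. That is fair, and it means one cannot say that the contrast is confounded, only that the set is unspecified. It does not remove the problem: the infection definition would still be open, and the power at 16 per arm would not be delivered.

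Second, the illustrative figures rest on assumed attack rates, response sizes and equal resting counts. Section 1.1 reports influenza-specific memory cells 2-4 times as frequent as RSV-specific ones in adult blood and lung, so equal resting counts are doubtful. This stands; it is why the 37% figure is given beside the 75%.

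Third, restricting to infected participants has its own bias. Hypothesis 2 credits T cells with helping to prevent infection, so the infected may be selected on baseline immunity, perhaps differently by virus. This also stands and shapes the remedy.

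Two stronger inferences are tempting but unsupported:
- A reader might argue that influenza infection rates must be higher, because section 1.8 excludes "Detectable baseline antibody titres against influenza challenge strains" and shows no RSV counterpart. A figure is missing from the supplied text directly before that line, and section 1.6.1 measures screening titres against both viruses. The absence of an RSV criterion cannot be relied on.
- A reader might turn the six-challenge series into a per-challenge non-infection rate for this trial. That series averages repeated re-challenges of previously infected adults and would need every subject to have had all six. It does not estimate infection at a first study challenge.

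**Conclusion.** The concern holds as an unspecified analysis set and an undefined infection status, with consequences under either reading.
- Infected only: power for 1.4 falls below the stated 80% once fewer than 15 per arm are infected. This rests only on the plan's own 1.4 and 1.3.
- All inoculated: the contrast is diluted, and it mixes attack rate with response if rates differ by virus. The size is illustrative. False positives stay at about 5-7% for equal or nearly equal rates and reach about 13-25% at 80% versus 50%. Power at 70/70 ranges from about 37% to about 75%, depending on the resting counts.

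The documents do not show that attack rates will differ, or how many participants will be uninfected. Treating this test as the primary comparison is an inference from its match to section 1.3, since the Statistics section labels no primary endpoint or timepoint. Placing it at the first challenge follows from section 1.10.3, where only the RSV arm is re-challenged.

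**What to change.** In Statistics and Data Analysis, before any T-cell data are seen:
1. Define infection from the nasal lavage already collected daily to day 10, stating the assay, the threshold and the window of days.
2. Pre-specify the RSV-versus-influenza comparison in infected participants of the first challenge, and report the all-inoculated comparison alongside it.
3. Analyse change from, or adjust for, the pre-inoculation T-cell count (blood and bronchoscopy samples are already planned before inoculation). This limits selection on baseline immunity but does not abolish it.
4. Report attack rates by arm.
5. Apply the same infection rule when choosing the 6 per group for the arrays.
6. Restate power for the number expected to be infected, with the attack-rate assumption written down. Use a standard deviation suited to the baseline-adjusted measure, which the documents do not give.

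The cost is wording and a revised power statement, with no extra samples. The downside should be stated openly: the main set is smaller, is selected after inoculation, and has lower stated power (for example 62.3% at 13 versus 8) unless more participants are inoculated.

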1.22. Ethics approval

The Chief Investigator has obtained approval from the Fulham Research Ethics Committee for this study. The study will be submitted for Site Specific Assessment (SSA) at Imperial College Healthcare NHS Trust. The Chief Investigator will require a copy of the R&D approval letter before accepting participants into the study. The study will be conducted in accordance with the recommendations for physicians involved in research on human subjects adopted by the 18th World Medical Assembly, Declaration of Helsinki 1964 and later revisions.

1.23. Consent

Consent to enter the study will be sought from each participant only after a full explanation has been given, an information leaflet offered, time allowed for consideration, and any questions participants may have answered. Signed participant consent will be obtained prior to any screening tests being carried out. The right of the participant to refuse to participate without giving reasons must be respected. After the participant has entered the study the clinician remains free to give alternative treatment to that specified in the protocol at any stage if he/she feels it is in the participant's best interest, but the reasons for doing so should be recorded. In these cases the participants remain within the study for the purposes of follow-up and data analysis. All participants are free to withdraw at any time from the protocol treatment without giving reasons and without prejudicing further treatment.

1.24. Confidentiality

The Chief Investigator and all of the research team will preserve the confidentiality of participants taking part in the study and abide by the Data Protection Act.

1.25. Indemnity

Imperial College, London as sponsor of this study holds negligent and non-negligent harm insurance policies which apply to this study. These have been arranged through the Joint Research Office.

1.26. Sponsor

Imperial College London will act as the main sponsor for this study. Delegated responsibilities will be assigned to the NHS trusts taking part in this study.

1.27. Funding

Following a successful Clinician Scientist Fellowship application the MRC is funding this study. They are acting as sole funders and this agreement is in place. The investigators will not receive any additional payment above their normal salaries. Participants in the study will have their travel costs refunded. They will also be given a donation of up to £3000 to compensate for the time and inconvenience of taking part in the study.

1.28. Audits and inspections

The study may be subject to inspection and audit by Imperial College London under their remit as sponsor and other regulatory bodies to ensure adherence to GCP and the NHS Research Governance Framework for Health and Social Care (3rd edition).

1.29. Sample storage and usage

Samples of tissue, cells and fluids will be stored at Imperial College London. Samples will be fully anonymised. These may be used for further assays or in other ethically approved studies. Samples may be shared with UK and international collaborators in studies that have been approved by local ethics committee and subject to a valid Materials Transfer Agreement.

STUDY MANAGEMENT

The day-to-day management of the study will be co-ordinated through [name], Clinical Senior Lecturer & Honorary Consultant in Infectious Diseases, with close support from [name]. In addition, a safety monitoring committee will convene monthly during the study to discuss all adverse events, protocol deviations, and other safety issues.

PUBLICATION POLICY

Our expectation is that after analysis the data from this study will be widely distributed in the medical and scientific community. Facilitated with presentations at local, national and international meetings, we hope to publish widely in the medical literature. In addition we have an excellent media department at Imperial College and publicise research that has public interest when it is published. No identifying participant information will be published.

REFERENCES

- 1 Thompson, W. *et al.* Estimates of US influenza-associated deaths made using four different methods. *Influenza Other Respi Viruses* **3**, 37-49 (2009).
- 2 Falsey, A. & Walsh, E. Respiratory syncytial virus infection in elderly adults. *Drugs Aging* **22**, 577-587 (2005).
- 3 Kreijtz, J. *et al.* Cross-recognition of avian H5N1 influenza virus by human cytotoxic T-lymphocyte populations directed to human influenza A virus. *J Virol* **82**, 5161-5166 (2008).
